6.1.2. Non-Measureable Lesions

Study Number: MCC 19178 IND#: Exempt

Non-Measurable Lesions are all other lesions or sites of disease. Measurements of these lesions are not required, but the presence or absence of each should be noted throughout follow-up.

- Complete Response (CR): The disappearance of all non-measureable lesions.
- Incomplete Response/Stable Disease (SD): The persistence of one or more non-measureable lesion(s). To be assigned a status of stable disease, measurements must have met the stable disease criteria at least once after study entry at a minimum interval of 8 weeks.
- Progressive Disease (PD): The appearance of one or more new lesion(s) and/or unequivocal progression of existing non-measureable lesions.

6.1.2. Notes on progression and new lesions

- For equivocal findings of progression (e.g. very small and uncertain new lesions; cystic changes or necrosis in existing lesions), treatment may continue until the next scheduled assessment. If at the next scheduled assessment, progression is confirmed, the date of progression should be the earlier date when progression was suspected.
- 2. A previous abnormal target lymph node that became normal and subsequently enlarged in size meeting the criteria for a pathologic and measurable lymph node (a short axis of ≥1.5 cm) should be added to the sum of diameters to determine if criteria for progression are met based on target lesions.
- A previously abnormal non-target lymph node that became normal and subsequently recurred must meet the criteria for progression based on non-target lesions to be considered progression.
- 4. A normal lymph node at baseline (<1.0 cm) that subsequently becomes pathologic is considered a new lesion and should be considered progression.
- 5. If newly abnormal lymph node(s) of unclear etiology is driving the progression event, continuation of treatment/follow-up and confirmation by a subsequent exam should be contemplated. If it becomes clear that the new lymph node has not resolved, is not resolving, or has increased in size, the date of progression would be the date the new lymph node was first documented as meeting pathologic criteria.

6.2. CENTRAL RADIOLOGY REVIEW

Baseline and response assessment radiology images will be evaluated along with historic images (CT, PET/CT, MRI collected from the time of diagnosis) for all evaluable patients enrolled at Moffitt Cancer Center. For patients who were enrolled at outside of Moffitt, baseline

and response assessment radiology images from patients with response will be submitted to Moffitt for central review to confirm response. For this purpose, the scans obtained at the time of best response will also need submitted. Please reference the Imaging Data Transmittal Form for additional submission details.

IND#: Exempt

7. ASSESSMENT OF SAFETY

Study Number: MCC 19178

7.1. ENDPOINTS OF SAFETY

Safety of cetuximab and nivolumab will be evaluated as indicated by intensity and incidence of adverse events, graded according to US NCI CTCAE Version 4.1. Safety endpoints include:

- Events leading to dose reduction
- Events leading to permanent treatment discontinuation
- The overall incidence and CTCAE v4.1 criteria grade of adverse events, as well as relatedness of adverse events to treatment
- · Causes of death

7.2. DEFINITIONS OF ADVERSE EVENTS

7.2.1. Adverse Event

An adverse event (AE) is defined as any untoward medical occurrence, including an exacerbation of a pre-existing condition, in a patient in a clinical investigation who received a pharmaceutical product. The event does not necessarily have to have a causal relation with this treatment. Lab abnormalities not deemed clinically significant will not be collected.

7.2.2. Serious Adverse Event

A serious adverse event (SAE) is defined as any AE that results in death, is immediately life-threatening, results in persistent or significant disability/incapacity, requires or prolongs patient hospitalization, is a congenital anomaly/birth defect, or is to be deemed serious for any other reason if it is an important medical event when based on appropriate medical judgement that may jeopardize the patient and may require medical or surgical intervention to prevent one of the other outcomes listed in the above definitions.

In addition, all reports of spontaneous abortion, abuse, and/or drug dependency shall be considered as SAEs for regulatory reporting purposes.

Patients may be hospitalized for administrative or social reasons during the study (e.g., days on which infusion takes place, long distance from home to site). These and other hospitalizations planned at the beginning of the study do not need to be reported as an SAE in case they have been reported at screening visit in the source data and have been performed as planned.

Any SAEs that occur during the screening period or after lead-in cetuximab monotherapy (Day -14 to Day -1 of Cycle 1) prior to the first dose of the cetuximab and nivolumab combination do not need to be reported.

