- ^{d.} Relevant medical history must include smoking status (current smoker, former smoker, never smoker), number of pack years, and year of smoking cessation. Relevant medical history will also include p16 status, if known. Historic radiologic assessments will also be accessed, in accordance with protocol section 6.2, to further characterize the disease under study and to contribute to exploratory objectives.
- ^{e.} CBC and diff (complete blood count and differential) include white blood cell count, absolute neutrophil count, hematocrit, hemoglobin, platelets, % lymphocytes, % monocytes, % neutrophils, other differentials. Safety labs may be collected up to 72 hours prior to dosing.
- f. Serum chemistries include a Complete Metabolic Panel (including Na, Cl, CO2, K, BUN, creatinine, Ca) AND Mg, Phos. Safety labs may be collected up to 72 hours prior to dosing.
- ^{g.} Liver function panel includes Alk Phos, total bilirubin, SGOT (AST), SGPT (ALT), total protein. Safety labs may be collected up to 72 hours prior to dosing.
- h. If tumor paraffin blocks (or sufficient slides) are not available, fresh biopsy will be obtained before the first treatment. If fresh biopsy is indicated, one core (or punch) will be collected in formalin and the second core (or punch) will be collected in liquid nitrogen. The end of treatment optional biopsy may be performed up to 30 days after the EOT visit as scheduling may require.
- ^{i.} Toxicity assessment: Common Terminology Criteria for Adverse Events (CTCAE) version 4.1 will be used. All toxicity grades (including grade 1) should be captured on the case report forms. All toxicities that occurred during treatment and until 30 days following completion of therapy should be followed until resolution.
- ¹ Tumor measurement: The same type of scan should be used for repeat measurements. The scans may be performed up to 7 days before the projected corresponding treatment visit. Scans in screening will include: CT- or MRI-neck, CT-chest, CT-abdomen, and CT-pelvis. Response scans can be limited to the anatomy of areas of known and suspected disease. Scans must be performed with contrast.

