7.2.4. Causal Relationship of Adverse Event

Study Number: MCC 19178 IND#: Exempt

 Medical judgment should be used to determine the relationship, considering all relevant factors, including pattern of reaction, temporal relationship, de-challenge or re-challenge, confounding factors such as concomitant medication, concomitant diseases and relevant history. Assessment of causal relationship should be recorded in the CRFs.

Yes: There is a reasonable causal relationship between the investigational product administered and the AE.

No: There is no reasonable causal relationship between the investigational product administered and the AE.

- Worsening of the underlying disease or of other pre-existing conditions will be recorded as an (S)AE in the CRF.
- Changes in vital signs, ECG, physical examination, and laboratory test results will be recorded as an (S)AE in the CRF, if they are judged clinically relevant by the investigator.

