7.2.5. Adverse Event and Serious Adverse Event Reporting

- Upon inclusion into the study, the patient's condition is assessed (e.g., documentation of history/concomitant diagnoses and diseases) and relevant changes from baseline are noted subsequently.
- All adverse events, serious and non-serious, occurring during the screening period or after lead-in cetuximab monotherapy (Day -14 to Day -1 of Cycle 1) prior to the first dose of the cetuximab and nivolumab combination do not need to be reported.
- All adverse events, serious and non-serious, occurring during the course of the combination of cetuximab and nivolumab treatment (i.e., from Cycle 1 Day 1 onward through the 100-day follow-up period) will be collected, documented, and reported to the sponsor by the investigator on the appropriate CRFs/SAE reporting forms.
- All adverse events will be followed for a minimum of 100 days after protocol treatment, except in cases where a study participant has started a new antineoplastic therapy. However, any SAE occurring after the start of a new treatment that is suspected to be related to study treatment by the investigator will be reported. To allow for this collection, the first Q3 month follow-up visit after the End of Treatment visit should be an in-clinic visit if possible for the patient to come to the clinic.
- Reporting will be done according to the specific definitions and instructions detailed in the "Adverse Event Reporting" section of the Investigator Site File.

 For each adverse event, the investigator will provide the onset date, end date, grade according to CTCAE v4.1, treatment required, outcome, seriousness, and action taken with the investigational drug. The investigator will determine the relationship of the investigational drug to all AEs as defined in Section 7.2.1.

IND#: Exempt

- Adverse events with onset within first administration of cetuximab therapy and 100 days after last administration of cetuximab will be considered as on treatment. All AEs, including those persisting after end of study treatment must be followed up until they have resolved or have been sufficiently characterized or the principal investigator decides to not further pursue them.
- Serious and non-serious adverse events occurring later than 100 days after last administration of trial drugs will only be reported in case they are considered drugrelated or trial (procedure) related.

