8.2. CORRELATIVE WITH BLOOD

Study Number: MCC 19178

Blood samples from participating sites external to Moffitt must be submitted with the submission form documenting the date of collection of the sample; the protocol number, the patient's case number, time point of study, and method of storage (for example, stored at -80°C). The frozen specimens can be stored at -80°C (-70°C to -90°C) until ready to ship. If a -80°C freezer is not available, samples can be stored short term in a -20°C freezer (non-frost-free refrigerator preferred) for up to 7 calendar days (please ship on Monday-Wednesday only).

Please refer to the laboratory manual for processing and shipment instructions.

Specimen collection summary for correlative studies (Samples can be batched and sent in one shipment)

Specimens for Correlative Studies			
Specimens taken from patient:	Collected when:	Submitted as:	Shipped:
A paraffin-embedded tissue of archival tissue taken before initiation of treatment	Pre-treatment	Paraffin-embedded tissue block, or unstained slides (see Lab Manual)	Block shipped ambient
Fresh frozen tissue of the primary or metastatic tumor taken before initiation of treatment (for research purposes only: OPTIONAL)	Pre-treatment	Frozen tumor in a 2 mL cryovial	Tumor sent frozen on dry ice via overnight carrier
A paraffin-embedded tissue of the primary or metastatic tumor (for	Post-treatment taken: 1) between day 8 and 15 of Cycle 1 and before	Paraffin-embedded tissue block	Block shipped ambient

[figure not shown]
research purposes only: OPTIONAL)	cetuximab and nivolumab treatment on Cycle 1 Day 15, 2) at the End of Treatment visit		
Fresh frozen tissue of the primary or metastatic tumor (for research purposes only: OPTIONAL)	Post-treatment taken; 1) between day 8 and 15 of Cycle 1 and before cetuximab and nivolumab treatment on Cycle 1 Day 15, 2) at the End of Treatment visit	Frozen tumor in a 2 mL cryovial	Tumor sent frozen on dry ice via overnight carrier
PLASMA: 10 mL of anticoagulated whole blood in EDTA tube (purple/ lavender top).	Pre-treatment and post-treatment taken: 1) between day 8 and 15 of Cycle 1 and before cetuximab and nivolumab treatment on Cycle 1 Day 15, 2) after 3 cycles of study drugs or 3 months from starting the treatment if off the study drugs, 3) at the End of Treatment visit 4) at the end of 2-year follow-up	Refer to Lab Manual for processing, storage, and shipping to Moffitt.	Plasma sent frozen on dry ice via overnight carrier

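### Screening SAEs are exempt from required reporting with no exception for trial procedures, although a biopsy for the trial can be taken in that window

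*Combined protocol and SAP*

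**What the plan says.** **The exemption.** Section 7.2.2 covers "Any SAEs that occur during the screening period", as well as those that follow the lead-in cetuximab dose, and says that such events "prior to the first dose of the cetuximab and nivolumab combination do not need to be reported". Section 7.2.5 says the same of "All adverse events, serious and non-serious, occurring during the screening period or after lead-in cetuximab monotherapy" and starts required collection at Cycle 1 Day 1. Neither section sets trial procedures apart.

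**The procedures.** The study calendar marks research tissue in the pre-therapy column, Day -42 to -15. The schema makes baseline tissue a requirement. Calendar footnote h adds: "If tumor paraffin blocks (or sufficient slides) are not available, fresh biopsy will be obtained before the first treatment", as two cores or punches. Section 8.1 also offers a biopsy before treatment, and the specimen table in section 8.2 lists "Fresh frozen tissue of the primary or metastatic tumor taken before initiation of treatment (for research purposes only: OPTIONAL").

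**The late rule.** For events more than 100 days after the last dose, section 7.2.5 says they "will only be reported in case they are considered drugrelated or trial (procedure) related". Deaths that late also remain reportable as SAEs if judged related to the drug or the trial.

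**Causality.** Section 7.2.4 offers Yes or No. Yes means: "There is a reasonable causal relationship between the investigational product administered and the AE". There is no counterpart for a trial procedure.

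**The concern.** A biopsy taken only because the trial needs tissue carries risk and offers the patient no treatment. If it causes a serious bleed, an infection or a death during screening, the safety sections do not require anyone to report it. The Protocol Monitoring Committee reviews patterns of adverse events each month (section 11.5.3), but nothing assures that this event reaches it. The plan regards procedure-related harm as worth reporting long after treatment has ended, and it gives no reason for dropping that rule at the start. What is at stake is the protection of patients and a complete account of what the trial's procedures cost them. The primary endpoint, the power and the DLT assessment are not affected.

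**Working it through.** The plan states no figure on this point, so the check sets the reporting rules beside the procedure schedule.

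| Period | Research procedure possible | Reporting required |
|---|---|---|
| Screening, Day -42 to -15 | Fresh biopsy if no archival tissue; optional research biopsy; blood | None |
| Lead-in, Day -14 to -1 | None marked in the calendar | None |
| Cycle 1 Day 1 to 100 days after treatment | Optional biopsies in Cycle 1 (from day 8, before Day 15 dosing) and at End of Treatment; blood | All AEs and SAEs; once a new antineoplastic therapy starts, SAEs suspected to be related to study treatment |
| Beyond 100 days | Blood at the end of 2-year follow-up | Events related to the drug or a trial procedure |

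**Does another section restore the duty at screening?**

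- Section 7.2.6 sets a 24-hour deadline for all SAEs. The same section takes AEs and SAEs as section 7.2.5 defines them, and section 7.2.5 contains the exemption. The only recipients it names are the two drug companies.
- Section 7.2.1 limits an adverse event to a patient who has been given a pharmaceutical product, and section 7.2.2 defines an SAE as a kind of AE. An injury before any study drug may therefore not be an SAE at all. That is a second way for it to fall outside the rules.
- The calendar marks a toxicity assessment at pre-therapy, and footnote i asks for all grades on the case report form. Its follow-up rule runs from treatment to 30 days after therapy. It creates no SAE report and no deadline.
- Section 11.5.3 makes the Protocol Chair responsible for reporting unexpected outcomes, and section 12.3.2 has sites submit a summary of unanticipated problems. Either could catch a case. Neither sets an SAE deadline, and a foreseeable biopsy complication might not qualify.

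So no section assures an SAE report or a 24-hour notice for a serious biopsy complication in screening.

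**Size.** The documents give neither the share of patients who will have a pre-treatment biopsy nor a complication rate. The planned number is 45 + 43 = 88 evaluable patients, before replacements. Purely as assumptions, take a biopsy share of 20% to 100% and a serious complication rate of 0.5% to 2%:

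- low: 88 × 0.20 × 0.005 = 0.09 events
- high: 88 × 1.00 × 0.02 = 1.76 events

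The range is almost twentyfold (1.76 / 0.088 = 20). The upper share is extreme, because archival tissue is the default and the other biopsy is optional. The range illustrates that few events are likely; it is not an estimate.

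**The case against.** The strongest reply is that starting collection at treatment is a deliberate choice that fits the definition in section 7.2.1, and that the exemption is permissive: it lifts a duty and forbids nothing. That is right. A reader might infer that a serious biopsy injury would go unreported and that the committee could not see it. The documents do not support that, given the other routes listed in the check. What stands is that none of them assures an SAE report.

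A reader might also infer that procedure-relatedness cannot be recorded at any visit. That is not established. Section 7.2.5 refers to an adverse event reporting section in the Investigator Site File, and neither that file nor the case report form is among the documents. The late rule itself presupposes that someone makes this judgement. What stands is that section 7.2.4, as written, covers only the product.

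The contrast with day 100 has a limit too. The End of Treatment visit is 30 days after the final dose (±3 days), and its biopsy may follow up to 30 days later. The last scheduled biopsy therefore falls near day 30 + 30 = 60, or day 63 with the window. The late rule is a general safeguard and does not show that an identical biopsy event is treated in two ways. The inconsistency is one of principle.

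Finally, a patient injured before Cycle 1 Day 1 may be non-evaluable and replaced. That follows from the evaluability rule in sections 3.2.4 and 10.1.2, and reporting the event would not change it.

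**Conclusion.** The point holds as a gap in required reporting. Sections 7.2.2 and 7.2.5 exempt every screening SAE without an exception for trial procedures, in a window where the protocol itself can call for a biopsy. This does not fit the rule that section 7.2.5 applies after day 100.

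The gap is narrow. It concerns patients without archival tissue and those who accept the optional biopsy. Few events are expected, and their number cannot be derived from the documents. The conclusion does not depend on the illustrative range; it rests on the text of the safety sections and assumes that the unseen Investigator Site File and case report form do not already close the gap. It is an inexpensive safety improvement and does not alter the efficacy design.

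The same exemption also covers events after the lead-in dose, while section 7.2.5 counts events from the first cetuximab administration as on treatment. That is a separate matter, and those passages must be reconciled with each other.

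**What to change.** - **Sections 7.2.2 and 7.2.5:** state that, from consent, any serious event considered related to a protocol-required or research-only procedure, including the pre-treatment biopsy, is reported within 24 hours to the coordinating center/Protocol Chair, and to the IRB per its policy. The recipient must be named, because section 7.2.6 names only the two drug companies for 24-hour reports.
- **Section 7.2.1:** extend the definition so that such an event counts before any study drug has been given. Without this, the new rule would contradict the definition.
- **Section 7.2.4:** add a second Yes/No item, related to a trial procedure, and carry it onto the case report form if it is not already there.

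Screening SAEs unrelated to trial procedures may stay exempt. The cost is a few sentences, one case report form item and a small number of extra reports.

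### Adverse events and SAEs, deaths included, after the Day -14 cetuximab dose and before Cycle 1 Day 1 are exempt from reporting, although Section 7.2.5 itself counts them as on treatment

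*Combined protocol and SAP*

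**What the plan says.** Section 7.2.2 exempts SAEs in screening, and those from Day -14 to Day -1 after the cetuximab lead-in, if they occur "prior to the first dose of the cetuximab and nivolumab combination do not need to be reported". Section 7.2.5 widens this to "All adverse events, serious and non-serious, occurring during the screening period or after lead-in cetuximab monotherapy". It then sets the window for what must be recorded: events "from Cycle 1 Day 1 onward through the 100-day follow-up period) will be collected, documented, and reported to the sponsor by the investigator".

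The same section also states: "Adverse events with onset within first administration of cetuximab therapy and 100 days after last administration of cetuximab will be considered as on treatment". It sets two other limits on reporting, and each keeps related events. Events later than 100 days after the last dose "will only be reported in case they are considered drugrelated or trial (procedure) related". After a new antineoplastic therapy has started, any SAE "that is suspected to be related to study treatment by the investigator will be reported".

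Section 7.1 lists the safety endpoints without mentioning the lead-in. They include overall adverse event incidence, grade and relatedness, causes of death, and "Events leading to permanent treatment discontinuation".

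**The concern.** Cetuximab is one of the two investigational drugs, and the Day -14 infusion is required of everyone. Section 3.2.1 gives its purpose as excluding patients with cetuximab hypersensitivity before the combination is assessed. Sections 4.1.1 and 5.1.5.1 foresee reactions that end cetuximab or remove the patient. The exempt window is therefore the one in which the protocol itself expects such reactions.

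What is at stake is safety reporting. A site that follows 7.2.2 and 7.2.5 as written need not tell the sponsor of a serious or fatal reaction to a study drug. If 7.2.6 is read through 7.2.5, it need not tell the two drug suppliers either. Patients lost in the lead-in are replaced (Section 3.2.4), and the toxicity table in Section 10.1.2 states neither a population nor a start date. It is therefore open whether these patients' events appear in any report.

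**Working it through.** The plan has no figure to reproduce here; the check compares the text.

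1. **When does on-treatment time start?** Section 7.2.5 says at the first cetuximab administration. Sections 4.1 and 4.3.1 put that at Day -14. An event on Day -13 is thus on treatment by one sentence of 7.2.5 and exempt by another.

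2. **Does the exemption reach deaths?** Yes. Section 7.2.2 defines an SAE to include an event that results in death, and the exemption covers any SAE in the window.

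3. **Do the endpoints allow for it?** Section 7.1 has no lead-in exception. A treatment-ending infusion reaction or a death on Day -13 falls under its plain wording, but no report of it is required.

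4. **How do the three limits in 7.2.5 compare?**

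| Period | Is a related SAE still reportable? |
|---|---|
| More than 100 days after last dose | Yes |
| After a new antineoplastic therapy | Yes |
| Day -14 to Day -1, after cetuximab | Need not be reported |

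5. **Is it needed for the DLT assessment?** No. Sections 4.2.3 and 10.1.1 exclude lead-in toxicity from the DLT count by their own rule and run the DLT period from Cycle 1 Day 1 to Day 28.

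6. **Does another rule restore reporting?**
 - Section 7.2.6 sends all SAEs to both suppliers within 24 hours, but its preceding sentence refers to AEs and SAEs as 7.2.5 defines them. The two readings conflict.
 - The 24-hour hypersensitivity rule in Section 4.5.1.1 stands under the nivolumab heading, and no nivolumab is given in the lead-in.
 - Section 4.4.3 asks for sponsor contact about a cetuximab reaction only where there is a question about it.
 - The study calendar marks a toxicity assessment at the lead-in, and footnote i wants all grades on the CRF. That mark may be pre-dose, and the row is also marked at pre-therapy, so this is a secondary tension.

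7. **Exposure.** Section 3.2.4 plans 45 + 43 = 88 evaluable patients; those treated at the MTD in phase I are within the 45. Day -14 to Day -1 is 14 days, so 88 x 14 = 1,232 patient-days. The documents do not say whether the calendar's ±3-day window applies to Cycle 1 Day 1. If it does, the range is 88 x 11 = 968 to 88 x 17 = 1,496. Replaced patients are additional. This is exposure, not an event count.

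**The case against.** The exclusion looks deliberate. It is stated twice with day limits, and it matches objectives framed around concurrent treatment. The on-treatment sentence classifies events and does not say which are reported. Section 7.1 sets no collection window, so it is silent rather than strictly contradictory. The 24-hour sentences in 7.2.6 can be read on their own, in which case lead-in SAEs do reach both suppliers.

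There are also partial backstops:
- the reason and date of removal on the CRF (3.3.4);
- follow-up of patients removed for adverse events (3.3.5, 9.1.4) and survival follow-up of all patients (9.1.4);
- grade and causality on the CRF (7.2.3, 7.2.4);
- the Protocol Chair's duty to report unexpected outcomes (11.5.3);
- site summaries of unanticipated problems (12.3.2).

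Section 7.2.5 further says that "Reporting will be done according to the specific definitions and instructions detailed in the" adverse event section of the Investigator Site File, which is not among the documents. Finally, the 88 evaluable patients all reached Cycle 1 Day 1, so none had a fatal lead-in event or one that stopped treatment before that day.

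Much of this stands as qualification. A lead-in death should appear in the survival data, some events may reach the CRF, and the 1,232 patient-days leave out the patients who matter most. But no section plainly overrides the exemption, and no backstop clearly secures a graded, causality-assessed report within 24 hours. A focus on the combination explains the DLT window; it does not explain why related serious events after a study-drug dose need not be reported.

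**Conclusion.** The concern holds, and the text must be corrected. The exemption is explicit, covers fatal events, and is at odds with the on-treatment definition in the same section. It is also the only one of the three limits in 7.2.5 that does not keep related events reportable.

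The nominal window is 14 days after one study-drug dose in every patient. The number of events that would go unreported cannot be stated, because neither the lead-in event rate nor the number of replaced patients is given. The conclusion is firm on the wording; what sites would actually report also depends on the unseen Investigator Site File and on how 7.2.6 is read. Nothing here implies bias in the survival endpoint or in the DLT result on which Dose Level 1 was chosen.

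**What to change.** - In 7.2.2 and 7.2.5, limit the exemption to the screening period before any study drug.
- Start AE and SAE collection and reporting at the Day -14 cetuximab dose, and change the 7.2.5 bullet that starts at Cycle 1 Day 1 to match.
- State in 7.2.6 that the 24-hour rule applies from the same point, and check that the Investigator Site File agrees.
- Leave the DLT window in 4.2.3 and 10.1.1 unchanged.
- In 10.1.2, tabulate toxicity for all patients who receive any dose of either drug, with lead-in events shown separately from combination events.

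The cost is protocol wording and somewhat more AE and SAE reporting. No visit is added: toxicity assessments are already scheduled every two weeks on treatment and at End of Treatment, where post-dose lead-in events can be recorded.
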